Harp's Pharmacy has a successful medication therapy management (MTM) program where pharmacists are provided time for patient-centered activities for patients with diabetes (DM), hypertension (HTN), the 2 leading causes for CKD, and heart failure (HF), the leading cause of death in CKD. Thirty six percent of patients with DM will develop CKD and hypertension can be both a cause and an effect of CKD (5). In this project they will use their MTM infrastructure to add CKD to their program in select pharmacies in the delta. The CKD tools build on and support actions that improve the underlying conditions that are already being addressed. The "CKD: What Your Need to Know" tools will be used with patients with known CKD or 2 of the 3 conditions covered by MTM and randomized into 1 of 3 education arms that offer various levels of support or a control arm.

Using non-nephrology clinicians to expand access to education earlier in their disease progress is essential. This project will inform how various levels of support provided by pharmacists and their staff using nephrology developed tools can effect patient choice allowing comparisons of support time and outcomes. Empowering patients to be proactive partners in their health care, through education and accountability, by choosing both their RRT and performance goals to protect their kidneys is key to improving outcomes. Demonstrating that non-nephrology clinicians can effectively educate and support these patients will provide models that other clinicians can use.

Minorities, especially in rural areas, are less likely to receive most kinds of care including evidence-based practices, home dialysis or transplantation (4,5). Developing patient-centered approaches to care such as this project can reduce disparities.

One-on-one outreach to educate and motivate patients and seek their feedback can strengthen commitment and adherence to medical regimens. Learning what to expect can promote self-management behaviors.

The AR Department of Health (ADH) Southeast (SE) region covers most of the Delta and was selected because it has the poorest outcomes for patients starting RRT. In 2017, new patients were predominately black (61%), less than half had seen a nephrologist prior to starting RRT, only 1.3% had seen a dietitian, most (92.3%) started hemodialysis using a catheter and 2.1% started on home peritoneal dialysis. Only 2.1% had no insurance (9). This data can be tracked annually to track impact.

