Harp's pharmacists will screen patients in their MTM program and enroll them in familial or peer clusters consisting of 1 or more subjects and randomize them into 1 of the 4 study arms using a site specific randomization schedule. Each arm will receive pre and post testing and health literacy evaluation. Two education arms will use the 139 page CKD: What You Need to Know workbook including the CKD Action Plan as self-study tools and follow-up during regular MTM appointment. The 3 arms include 2 education arms and a control arm with various levels of intervention: Arm 1) case management model including pharmacist initiated discussion of workbook content and action plan reinforcement, Arm 2) brief introduction of the workbook and action plan reinforcement, Arm and Arm 3) the control group will receive a list of web-based CKD sites and a copy of the action plan with no additional intervention. Patient initiated CKD discussions will be tracked by both the pharmacist and staff by topic and time spent. Time spent by the pharmacist and staff will be calculated along with outcomes and compared in each group. Data collected upon enrollment will include year of birth, race, gender, county of residence, history of CKD, diabetes, hypertension and/or heart failure, patient reported blood pressure, AIC, eGFR and hemoglobin, smoking history, renal transplant history and if is under the care of or has been seen by a nephrologist in the past.

The CKD: What You Need to Know Workbook is 139 pages and includes:

- An Introduction
- 8 Chapters plus resources:
 1. Kidneys and Chronic Kidney Disease (CKD)
 2. Protecting Your kidneys and Slowing CKD Progression
 3. Your Choices for Dialysis and Transplantation
 4. Lab Results: What they mean & What you can control
 5. Chronic Kidney Disease & Eating Habits

6. Chronic Kidney Disease & Meds
7. Learning to Cope with Kidney Disease
8. Paying for Your CKD Treatment
9. CKD Action Plan
10. Web-based Resources
11. Kidney Talk: What do these words mean?
12. Resources

Each section ends with “Frequently Asked Questions”, “Test Your Knowledge” and has space for notes. Patient testimonies are found at the back of 6 chapters.

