The workbook went through health literacy editing with a goal of a 5th grade reading level. The chapters ranged from 3rd to 7th grade levels. It was felt that it was important for subjects to learn or at least be exposed to words that were kidney related and frequently used by their health care providers. So the first time each of these words were used in the workbook they were red and the definition was in the kidney talk section on that page. Then the first time the word appeared in subsequent chapters the word was in red but no definition was on that page.

Subjects will be randomized into 1 of 2 education arms that offer various levels of support or a control arm using a site specific computer generated randomization schedule. Presumed monthly visits.

Study Arm	Handouts	Visit 1*	Visit 2	Visit 3	End of Study June 2022
Testing		Pre-test		Post-Test	Evaluation
1: Case Study Model	Workbook Action Plan (V1) Label reading Exercise (V2)	Pharmacist initiated review of workbook and assist with Action Plan goal selection	Action Plan Reinforcement. Discuss Chapters 1-4. Provide “Label Reading Exercise”	Action Plan Reinforcement. Discuss Chapters 5-8 and resources. Review results of Label exercise	Open conversations from each party for all arms after evaluation
2: Minimal Instruction	Workbook Action Plan	Briefly explain handouts with focus on Action Plan.(5-10 minutes)	Action Plan Reinforcement. Answer patient’s questions.	Action Plan Reinforcement. Answer patient’s questions.	As Above
3: Control	Resource List Action Plan	Answer patient’s questions.	Answer patient’s questions.	Answer patient’s questions.	As Above

*On first visit, education arms subjects will be asked to read 1 chapter of the workbook weekly. All subjects will receive a CKD Action Plan and be asked to set individual goals.

Secondary outcome data collected at each visit include both self-reported and/or

Title: Pragmatic Approach to Chronic Kidney Disease Education in the Delta V.6

PI: [name]

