pharmacist or physician confirmed blood pressure and AIC, eGFR, hemoglobin. Patient and/or pharmacist initiated CKD conversation and topics including CKD action plan goal progress. The action plan has 1 knowledge goal related to CKD cause, eGFR and trend and 10 performance goals based on international guidelines and best practices including AIC goal of 7 or less, blood pressure goal of less than 140/90, exercise goal of 30 minutes 5 times a week, medications that may need to be avoided (ex: ibuprofen) or may need to be taken (ex: Statin) if you have CKD and DM or over 50 years old), smoking cessation, kidney friendly diet (may need to modify salt, phosphorus and/or protein intake and be edema free [may require monitoring and adjust salt and water intake], home monitoring of blood pressure, blood sugar and weight, weight management and anemia (goal hemoglobin above 10g/dL)

Study Population

High Risk Subjects will be identified from the Harps MTM program or others having multiple known medical problems (CKD, HTN, DM or heart disease). Know Your Kidney Number Posters which will be available statewide by the time the study starts will be posted in the pharmacy. Even though they are not study specific, they provide pertinent CKD information that could motivate subjects to want to learn more about how to protect their kidneys. Study Patient information Sheets will be available for interested parties.

A total of 100 clusters of 1 or more people from familial or peers groups will be enrolled. The actual number of subjects will depend on the volume of clusters with more than 1 person. This would include approximately 1/3 of the Harps MTM subjects that have both DM and HTN.

Inclusion Criteria

- Adults (any gender)>18 years old
- Enrolled in Harp's MTM program
- Has Known CKD or 2 of the 3 conditions covered in MTM (DM, HTN and Heart Failure)
- Not on dialysis

Exclusion Criteria

- unable to read or speak English
- history of significant cognitive dysfunction unless qualified caregiver is the one being educated
- not personally independent or without any social support

Risks and Benefits

A risk to study participants is the potential for loss of confidentiality of study data.

Measures to protect the confidentiality of study data will be implemented as described in the Data Handling and Recordkeeping section below.

Title: Pragmatic Approach to Chronic Kidney Disease Education in the Delta V.6

PI: [name]

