Know workbook, slide sets, CKD action plan, Label reading exercise, Web-based resource list, data collection sheets, pre and post tests and program evaluation. UAMS staff will participate in the initial education of Harps staff and future education, as requested. UAMS will make the 10 points of CKD Care for Primary Care Providers (PCPs) available to both Harps staff and local PCPs, as requested.

Harps oversight staff and UAMS research staff will have monthly web-based or face to face meetings, with additional communication as needed.

Reporting requirements are the same for each site and outlined in the data section above. A central site may be selected by Harps when the sites are selected and serve as a model or mentoring site.

Data Analysis

Study arms will be compared by RRT choice using logistic regression that includes covariates found to differ between the groups. Results will be reported in terms of odds ratios and their 95% confidence intervals. Each group will be compared on the ability to choose a modality by the end of their 2nd or 3rd MTM visit, depending on their study arm and at the end of the study (June 2022) by comparing pre and post testing and program evaluation answers. To ensure balance in patient characteristics across clusters chi-square or Fisher's exact test, as appropriate, will be used to evaluate categorical measures, whereas two-sample t-test or Wilcoxon rank test, as appropriate, will be used for continuous measures.

The primary study aim is the ability of the participants to choose a dialysis modality by the end of their second or third visit, depending on their study arm. Descriptive statistics will be used to examine the trend in the patients' ability to choose a dialysis modality, level of interest in kidney transplant, the selection of a possible donor and having enough information to decide across the two assessment periods.

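### The plan gives both four and three as the number of arms, defines only three, and times the primary outcome by arm although the visit table has one common post-test visit

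*Combined protocol and SAP*

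**What the plan says.** **Number of arms.** Two places give four:

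- The background text before Specific Aims says that patients will be "randomized into 1 of 3 education arms that offer various levels of support or a control arm", which is three education arms plus one control.
- The sentence in Study Design and Procedures on screening and enrolling clusters says that pharmacists will "randomize them into 1 of the 4 study arms using a site specific randomization schedule".

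The remainder of Study Design and Procedures gives three:

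- A little further on in the same paragraph: "The 3 arms include 2 education arms and a control arm with various levels of intervention". The list that follows is numbered 1 to 3. It contains a broken fragment just before its last item: "Arm and Arm 3) the control group will receive a list of web-based CKD sites".
- Above the visit table: "Subjects will be randomized into 1 of 2 education arms that offer various levels of support or a control arm", done "using a site specific computer generated randomization schedule".
- The visit table has rows for Arms 1, 2 and 3 only, and row 3 is the control.

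Study Population sets the size: "A total of 100 clusters of 1 or more people from familial or peers groups will be enrolled". No section states an allocation ratio. Data Analysis refers to the arms without saying how many there are.

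**Timing of the primary outcome.** Data Analysis compares the groups on the ability to choose a modality "by the end of their 2nd or 3rd MTM visit, depending on their study arm". Its next paragraph repeats the same arm-dependent timing when it restates the primary aim. The testing row of the visit table has a pre-test at Visit 1, nothing at Visit 2, a post-test at Visit 3 and an evaluation at the end of the study. It makes no distinction by arm.

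**The concern.** The number of arms is a basic input to randomisation. It fixes how many codes a schedule contains, how many clusters each arm receives and how many between-arm contrasts the logistic regression can produce. It also enters the identifier: under Data Handling and Recordkeeping, the arm number is part of every study number. Here one document holds two randomisation instructions for the same kind of site-specific schedule, and they give different counts. A schedule with four codes would assign some clusters to an arm for which no handout, visit content or support level is described.

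The timing wording matters for a different reason. If the primary outcome were read at the second visit in one arm and the third in another, the arm comparison would mix the effect of the intervention with an extra visit of exposure. The plan presumes monthly visits and asks the education arms to read a chapter a week. An extra visit is therefore about a month of reading and one more pharmacist contact.

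**Working it through.** **Step 1. Count the arms.**

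| Place | Wording gives | Total |
|---|---|---|
| Background, before Specific Aims | 3 education + 1 control | 4 |
| Study Design and Procedures, enrolment sentence | 4 study arms | 4 |
| Study Design and Procedures, arm list | 2 education + 1 control, numbered 1 to 3 | 3 |
| Study Design and Procedures, second randomisation sentence | 2 education + 1 control | 3 |
| Visit table | rows 1, 2, 3 | 3 |

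The stated figure of 4 is not reproduced by counting the arms that have a described intervention. That count is 3.

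**Step 2. Consequence for the 100 clusters.** The plan gives no clusters per arm and no ratio, so this step rests on assumed ratios.

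- Three arms, equal allocation: 100 / 3 = 33.3, so about 33 clusters per arm and none without an intervention.
- Four arms, equal allocation: 100 / 4 = 25 per arm. One arm is undefined, so 25 clusters have no described intervention. With simple (unrestricted) randomisation at probability 0.25, the central 95% binomial range for that arm is 17 to 34 clusters.
- Four arms, other ratios, with the undefined arm last: clusters affected = 100 × (its share) / (sum of shares).

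| Assumed ratio | Calculation | Clusters without an intervention |
|---|---|---|
| 3:3:3:1 | 100 × 1/10 | 10 |
| 2:2:2:1 | 100 × 1/7 | about 14 |
| 2:1:1:1 | 100 × 1/5 | 20 |
| 1:1:1:1 | 100 × 1/4 | 25 |
| 1:1:1:2 | 100 × 2/5 | 40 |
| Three-arm schedule, any ratio | no fourth code | 0 |

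**Step 3. Contrasts.** Pairwise comparisons among k arms number k(k − 1)/2. That is 3 × 2 / 2 = 3 with three arms and 4 × 3 / 2 = 6 with four.

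**Step 4. Timing.** Data Analysis allows the second or the third visit, by arm, and states this twice. It does not say which arm has which visit. The visit table schedules no test at Visit 2 in any arm, so an outcome read at Visit 2 would have no scheduled post-test behind it. In Arm 1 the table places Chapters 1 to 4 at Visit 2 and Chapters 5 to 8 at Visit 3, so the amount of education delivered also differs between those two points. The two statements and the table cannot all be followed.

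**The case against.** The strongest reply is that the procedural text largely settles the count. The paragraph with the four-arm sentence goes on to describe three arms and number them. The second randomisation sentence, the only one to mention computer generation, gives three, and the visit table sits directly below it. Anyone trying to code a fourth arm would find nothing to code. This reply stands to a large extent: three is plainly the better-supported count, and the likely consequence in practice is small. It does not remove the contradiction from an operative instruction. The schedules are site specific, the sites are overseen by the pharmacy chain's own staff, and the plan describes no check of the schedules.

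Some stronger readings are tempting, and the documents do not support them:

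- *A quarter of the clusters will be lost.* This needs both a four-arm schedule and equal allocation. No ratio is stated, and no schedule of either kind is shown.
- *Site schedules are generated from the four-arm sentence.* No section says so, and the three-arm sentence has at least an equal claim.
- *The trial loses power.* Data Analysis says that the sample size was set by what was feasible and that power was secondary, so there is no planned power to lose. The home dialysis rates quoted there are for patients starting renal replacement, whereas this trial enrols people not on dialysis and asks about the ability to choose a modality.
- *The timing phrase and the broken fragment in the arm list are left over from a deleted arm.* Both are consistent with that, but it is inference.

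**Conclusion.** The inconsistency is real and lies in current text. Two places give four arms, the rest of the design text gives three, and only three are defined. The size of the consequence is conditional: about 25 of 100 clusters without a defined intervention if a four-arm schedule with equal allocation were used, 10 to 40 under the other ratios tried, and none if schedules follow the three-arm sentence. These figures count clusters, not people, because cluster sizes are not fixed.

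The timing conflict stands on its own and does not depend on the arm count. As written, Data Analysis permits the primary outcome to be assessed at different visits in different arms, while the visit table gives one post-test visit for all. Neither point shows that anything has gone wrong in conduct. Both are worth correcting because they touch allocation and the primary comparison and cost little to repair.

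**What to change.** 1. In Study Design and Procedures, change the enrolment sentence to three study arms, and complete or delete the broken fragment before Arm 3. In the background text, change three education arms to two.
2. State the allocation ratio and that it applies to clusters. An example is 1:1:1, for the sponsor to confirm. With 100 clusters that is about 33 per arm overall, though separate site schedules will not guarantee an exact split.
3. Check that every site schedule, and every study number already issued, uses only arm codes 1 to 3, and record the check.
4. In both places in Data Analysis, replace the whole second-or-third-visit, arm-dependent wording with the common Visit 3 post-test, so that the primary outcome is assessed at the same visit in all arms. Removing only the reference to study arm would leave the choice between two visits open. The separate end-of-study comparison can stay as it is.

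The cost is a text correction and a check of the site schedules. No new data collection and no change to the sample size are needed.

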The tools being used were developed by a multidisciplinary team of nephrology experts which are limited in the delta. Courses including train the trainer classes for pharmacies and 10 points of Care for CKD for clinicians will be conducted. Collaboration with local providers can both educate and promote community engagement.

Harp pharmacists expressed randomization concerns. They report that many of their MTM subjects have multiple family members or friends enrolled in the study. This could confound randomization into various arms since these subjects are highly likely to compare and contrast the details of their intervention. It was decided that a cluster randomization schedule would be utilized with each cluster self-selecting a leader that would be enrolled in the study and be responsible for education of the other cluster

members. All cluster members will undergo the same testing.

Specific Aims

The primary aim is to assess the effectiveness of pharmacists and their staff to educate CKD and high risk patients evaluating effectiveness through patient choice of RRT in each arm (e.g. home dialysis choice rate). Secondary aims include 1) Identify actions patients are willing to take to protect their kidney function using the CKD Action Plan that contains 10 performance goals based on international CKD guidelines that can slow CKD progression 2). Describe outcomes and methods used by peer leaders to educate cluster members using the same goals. 4) Compare costs (based on pharmacist and pharmacy associate time) with outcomes in each arm.

Study Design and Procedures

This study is a randomized control pilot study using non-nephrology clinicians to educate patients who are at high risk for CKD how to protect their kidneys and be ready for RRT if and when needed by utilizing nephrology developed educational tools.

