Secondary outcomes will be compared in all clusters. Because randomization seldom results in samples that are balanced on all baseline characteristics, information on control variables relevant to choice of dialysis mode will be collected, including age, gender, baseline intent to start home based dialysis, whether currently being followed by a nephrologist, patient engagement measured by the percent of visits where CKD patient initiated discussion took place and self-reported and provider confirmed outcomes listed in study plan. Pharmacists and staff time will be compared between arms and linked to costs to support each intervention arm. Tests appropriate for the measure will be used when comparing baseline characteristics between the research arms.

The sample size was based on what was appropriate for what could be reasonably be accomplished in the time frame with the available funding. Power based on the primary aim was a secondary consideration. A population of 100 clusters could result in a much larger population of subjects depending on the size of the clusters. Utilizing clusters to essentially train peer educators and describe their training methods, as well as, the outcomes of each of their cluster members can inform future research involving CKD peer educator led CKD patient education programs.

Ethical Considerations

This study will be conducted in accordance with all applicable government regulations and University of Arkansas for Medical Sciences research policies and procedures. This protocol and any amendments will be submitted and approved by the UAMS Institutional Review Board (IRB) to conduct the study.

This study meets the criteria for exempt review and does not require formal consent of the subjects. However, a Patient Information Sheet explaining the study will be provided to interested parties. After discussion with Harp's pharmacist, verbal consent will be obtained and completion of the pre-test will be evidence of consent. UAMS will receive no HIPAA data on subjects. All data will be de-identified as outlined above and a HIPPA waiver has been requested.

Dissemination of Data

Results of this study may be used for presentations, posters, or publications. The publications will not contain any identifiable information that could be linked to a participant.

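### The primary logistic model ignores the randomised family or peer cluster, so its intervals are too narrow when members' answers are correlated; randomising site should also be named, for efficiency only

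*Combined protocol and SAP*

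**What the plan says.** All references are to the combined protocol and SAP.

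- **Unit of randomisation.** The background text before Specific Aims records the pharmacists' report that "many of their MTM subjects have multiple family members or friends enrolled in the study". It then states: "It was decided that a cluster randomization schedule would be utilized with each cluster self-selecting a leader". The leader educates the other members, and "All cluster members will undergo the same testing".
- **Schedule.** Study Design and Procedures says that staff will "randomize them into 1 of the 4 study arms using a site specific randomization schedule". The text above the visit table has subjects allocated to two education arms or control "using a site specific computer generated randomization schedule". The number of sites and any blocking are not given.
- **Primary model.** Data Analysis says: "Study arms will be compared by RRT choice using logistic regression that includes covariates found to differ between the groups". Results are odds ratios with 95% intervals. No threshold for a difference is given. The balance tests concern patient characteristics, and their unit (subject or cluster) is not stated.
- **Control variables.** Data Analysis says that "information on control variables relevant to choice of dialysis mode will be collected, including age, gender, baseline intent to start home based dialysis"; the list continues without site.
- **Size.** Study Population plans 100 clusters and leaves the number of subjects open. Data Analysis adds: "Power based on the primary aim was a secondary consideration".
- **Identifiers.** Data Handling and Recordkeeping puts site, enrolment number and member number in each study number. Its worked example is a two-person cluster.

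**The concern.** Members of a cluster share an arm, a leader who teaches them and often a household, so their RRT choices are plausibly correlated. An ordinary logistic regression counts each member as an independent observation. The standard error of the arm effect is then too small, and the primary odds ratio looks more precise than it is.

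Site raises a lesser question. Allocation is done within site, yet site can enter the model only through a rule based on observed imbalance. Whether it enters would depend on blocking, test unit and threshold, none of which is stated. What is at stake there is some power and the meaning of the odds ratio, not validity.

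**Working it through.** **Inputs.** The plan gives 100 clusters, site-specific schedules and 95% intervals. It gives no power, intracluster correlation, number of sites or cluster-size distribution, so there is no planned figure to reproduce. I take three arms, as in the visit table: about 33 clusters per arm and 65-66 in a two-arm contrast. Assumed: 35% choosing at an average cluster, family SD 1.0 to 1.5 (0.6 as a low case), site SD 0.5 to 1.0, all on the logit scale.

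**1. Correlation between members.** With π(u) = expit(logit 0.35 + u) and u normal with SD s, the correlation is ρ = Var(π)/[p̄(1 − p̄)]. Numerical integration gives ρ = 0.072 (s = 0.6), 0.167 (s = 1.0) and 0.288 (s = 1.5).

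**2. Effect on the test.** Design effect DE = 1 + (Σm²/Σm − 1)ρ, with m the cluster size. Σm²/Σm is 5/3 for half pairs, 2 for all pairs and 30/10 = 3 for equal shares of sizes one to four. A nominal 5% test that ignores clustering rejects with probability 2Φ(−1.96/√DE).

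| Cluster sizes | s = 0.6: DE, null | s = 1.0: DE, null | s = 1.5: DE, null |
|---|---|---|---|
| Half pairs | 1.048, 5.6% | 1.112, 6.3% | 1.192, 7.3% |
| All pairs | 1.072, 5.8% | 1.167, 7.0% | 1.288, 8.4% |
| Sizes 1-4 | 1.145, 6.7% | 1.335, 9.0% | 1.576, 11.8% |

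At s = 1.0 to 1.5, correct intervals would be wider by a factor √DE, from √1.112 = 1.05 to √1.576 = 1.26.

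**3. Simulation.** Two-arm null runs at family SD 1.0 to 1.5 agree: about 6-9% with half or all pairs and 9-12% with sizes one to four, against 3-5% with cluster-robust errors. A separate three-arm simulation (100 clusters, five sites, blocks of six, mean size 2.5, site SD 0.5, 3,000 runs) gave these null rejection rates:

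| Latent ICC | As written | Site only | Site + cluster-robust |
|---|---|---|---|
| 0.10 | 5.7% | 6.2% | 6.0% |
| 0.30 | 9.3% | 10.0% | 6.2% |
| 0.55 | 14.0% | 14.6% | 6.3% |

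Site alone does not help. The last column used only a K/(K − 1) factor (K = clusters) and the normal critical value, which is why a small-sample correction is wanted.

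**4. Would the imbalance rule bring site in?** Chi-square test of site by arm at 5%, 100 clusters, three arms, 3 to 10 sites:

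- blocks of three or six, cluster-level test: 0%;
- simple allocation, cluster-level test: 4.5-5.1%;
- simple allocation, subject-level test: 23-51% with half pairs and 32-73% with all pairs, because members who share site and arm are counted as independent;
- only the listed patient characteristics tested: never.

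**5. Cost of omitting site** (one-person clusters, five sites of 13).

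- *Null rejection without site:* 3.4-5.2%, so no inflation.
- *Odds ratio:* at 35% and a within-site OR of 4, averaging over a site SD of 1.0 gives rates of 0.3745 and 0.6540. The marginal OR is (0.6540/0.3460)/(0.3745/0.6255) = 3.16. At SD 0.5 it is 3.71. For 10% versus 44%, the within-site OR is (0.44/0.56)/(0.10/0.90) = 7.07, which becomes 6.51 (SD 0.5) or 5.30 (SD 1.0).
- *Power without and with a site random intercept, 35% and OR 4:* SD 0.5, 71.9 to 73.0% blocked and 72.9 to 73.3% simple; SD 1.0, 63.3 to 68.1% and 62.0 to 65.2%.
- *10% versus 44%:* SD 0.5, 82.4 to 82.7% and 82.1 to 82.8%; SD 1.0, 80.2 to 82.1% and 78.7 to 80.1%.
- *Scale:* SD 1.0 is wide. With a 35% average, 95% of sites would lie between 7% and 79%.
- *Other assumptions:* the three-arm simulation, with one-person clusters, fixed site terms and OR 3, showed larger gains: 54 to 57% (SD 0.5) and 45 to 52% (SD 1.0).

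**The case against.** **This is a pilot sized by feasibility, and most clusters may be single.** If so, the model as written is nearly correct. This stands as a condition on size: the inflation needs both multi-person clusters and real correlation. But the plan adopted cluster randomisation because relatives and friends take part together, and it expects that the clusters could yield many more than 100 subjects.

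**The primary analysis may be meant for leaders only.** Specific Aims treats members' outcomes as something to describe. One person per cluster would remove the problem. The plan does not say this: members are called subjects, are tested alike, and no restriction appears in Data Analysis.

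**A reader might infer that the imbalance rule would nearly always leave site out.** The documents do not support that without conditions. It holds if schedules are blocked, if the test is at cluster level, or if only the listed characteristics are tested. With unblocked schedules and subject-level tests, site could be flagged often, though only by chance.

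**A reader might also infer that omitting site biases the result.** It does not. The odds ratio without site is a valid marginal quantity, and cluster-robust errors alone restore the error rate (3.6-5.2% without a site term in runs with half pairs, all pairs and sizes one to four). The site element is therefore an efficiency gain.

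**The 10% and 44% rates are home-dialysis rates among patients starting RRT**, whereas Data Analysis states the primary aim as the ability to choose a modality. That is fair; they are illustrative, and the cluster result does not use them.

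**Conclusion.** The concern holds, with the cluster as the main point. Followed as written, the primary model gives 95% intervals that are too narrow whenever multi-person clusters are correlated: null rejection of about 6-9% with half or all pairs and 9-12% with sizes one to four, at an assumed family SD of 1.0 to 1.5. The effect is negligible at low correlation or with nearly all single clusters. The plan gives neither the sizes nor the correlation, so the actual inflation is unknown.

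Naming site is a cheap secondary improvement. In the main layout it is worth about 0-1 point of power at a site SD of 0.5 and 1-5 points at 1.0. It should not be added without the cluster correction. The calculations assume three arms; the documents give four in one place and three in others, and these must be reconciled.

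**What to change.** Add to Data Analysis:

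> The primary logistic model uses cluster-robust standard errors (or GEE) at the level of the randomised family or peer cluster, with a standard small-sample correction, and includes randomising site irrespective of observed balance (as a random intercept, or with small sites pooled, if sites are many). The odds ratio without site is reported as a secondary, marginal estimate, also with cluster-robust errors.

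Also state the number of sites, whether the site schedules are blocked, whether all tested members enter the primary analysis, and the number of arms.

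**Cost.** A few sentences and no new data. The odds ratio becomes conditional on site. Intervals widen when clusters have more than one member: in the three-arm simulation (mean size 2.5, latent ICC 0.30, site SD 0.5, OR 3), power went from 72.5% as written to 63.8% with site and cluster-robust errors, but the higher figure came with 9.3% null rejection. Robust errors beside a site random intercept may need custom code or a bootstrap of whole clusters within site. A correction that charges one degree of freedom per site is best avoided: with 22 sites of three clusters (half pairs), null rejection fell to 2.4%, against 4.1% for cluster-robust errors without site.
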